15. SPONSORSHIP AND INSURANCE

The University has a specialist insurance policy in place which would operate in the event of any participant suffering harm as a result of their involvement in the research (Newline Underwriting Management Ltd, at Lloyd's of London).

16. FUNDER

The funder, Shanghai Fosun Pharmaceutical Industrial Development Co., Ltd, had a role in the design of the study. The funder will not have any role in its execution, analyses, and interpretation of data or decision to submit results.

17. PUBLICATION POLICY

Any data published in the peer-reviewed medical literature will protect the identity of the patients. This trial will be registered in a web-based protocol registration scheme. All those who have made a substantial contribution will be co-authors on publications. The sites have the right to publish their data individually and to include members of the sponsor's team who have made a significant contribution. There will also be publications of pooled data which will be coordinated by the MORU group. All sites will have the opportunity to contribute to these publications.

The research findings disseminated to policy makers, National Malaria Control Programmes (NMCPs) and other researchers.

APPENDIX 1. DOSING SCHEDULES

The dosing scheme for parenteral artesunate is 2.4 mg/kg at hour 0, hour 12, hour 24, and each 24 hours until the patient can take oral medication. Children <20 kg will get 3.0 mg/kg. At least 3 parenteral doses should be given before switching to oral therapy can be considered i.e.: stop injectable artesunate and give oral antimalarial. When the patient is improving and able to take oral tablets a switch to oral ACT should be considered.

2-step conventional injectable artesunate. Refer to Artesun SmPC page 2&3.

One unit box of Artesun (conventional injectable artesunate) contains:

Each vial contains: artesunate powder 60 mg

Each ampoule of solvent contains: sodium bicarbonate 50 mg/ml, 1 ml

Each ampoule of diluent contains: sodium chloride 9 mg/ml, 5ml (There is no need to use additional 5% dextrose for dilution.)

For intravenous (IV) injection (10 mg/ml)

After reconstitution and dilution one ml of solution for injection contains 10 mg artesunate.

Using a syringe, add 5 ml of sodium chloride 0.9% for injection to the vial containing the reconstituted artesunate solution. This will yield 6 ml of a solution containing artesunate 10 mg/ml. Shake to mix well, ensuring that the resulting solution is still clear. If the solution appears cloudy or a precipitate is present, it should be discarded.

The volume of the solution required (ml) will be:

Volume (ml) = [dose (mg)] ÷ 10

For intramuscular (IM) injection (20 mg/ml)

After reconstitution and dilution one ml of solution for injection contains 20 mg artesunate.

Using a syringe, add 2 ml of sodium chloride 0.9% for injection to the vial containing the reconstituted artesunate solution. This will yield 3 ml of a solution containing artesunate 20 mg/ml. Shake to mix well, ensuring that the resulting solution is still clear. If the solution appears cloudy or a precipitate is present, it should be discarded.

The volume of the solution required (ml) will be:

Volume (ml) = [dose (mg)] ÷ 20

1-step injectable artesunate. Refer to Argesun SmPC page 2&3.

Dose: Adults and children weighing more 20 kg or more: 60mg is administered at a dose of 2.4mg of artesunate / kg body weight, by intravenous (IV) or intramuscular (IM) injection, at 0, 12 and 24 hours, then once daily until oral treatment can be substituted. Children weighing less than 20 kg: 60mg is administered at a dose of 3 mg of artesunate/kg body weight, by intravenous (IV) or intramuscular (IM) injection, at 0, 12 and 24 hours, then once daily until oral treatment can be substituted (see section 5.1).

New injectable artesunate (Argesun®) 60mg should be administered for a minimum of 24 hours (3 doses), regardless of the patient's ability to tolerate oral medication earlier. After at least 24 hours of Argesun® 60mg and when able to tolerate oral medication, the patient should be switched to a complete treatment course of an oral antimalarial regimen.

Preparation

Because of the instability of artesunate in aqueous solutions, the reconstituted solution must be used within one hour of preparation. Therefore, the required dose of artesunate should be calculated (dose in mg = patient's weight in kg x 2.4 for patients weighing more than 20 kg; or dose in mg = patient's weight in kg x 3 for children weighing less than 20 kg) and the number of vials of artesunate needed

should be determined prior to reconstituting the artesunate powder.

Reconstitution of the artesunate solution Following reconstitution the solution must be diluted according to the method of injection, as described below.

For intravenous (IV) injection & intramuscular (IM) injection (20 mg/ml), using a syringe, withdraw 3 ml of the sodium bicarbonate and arginine solvent, which is half the volume of the ampoule, and inject this into the vial containing the artesunate powder. Gently shake the vial for up to 3-5 minutes or until the powder is completely dissolved and the solution is clear. If the solution appears cloudy or a precipitate is present, it should be discarded. The reconstituted artesunate solution should always be used immediately, and discarded if not used within one hour. The end concentration of the solution will be 20 mg artesunate per ml solvent. Thus, the volume in ml for administration to the patient will be equal to: $(\text{desired dose in mg})/20$

Withdraw the required volume of artesunate solution from the vial with a syringe and then administer to the patient by slow intravenous or intramuscular injection over 1-2 minutes. New injectable artesunate (Argesun[®]) 60mg should NOT be administered as an intravenous drip. Reconstituted vials of Artesunate for Injection and ampoules of the solvent Sodium bicarbonate and Arginine injection are for single use only. Discard unused portions. Do not use water for injection for reconstitution of the artesunate powder or for dilution of the resulting solution prior to injection.

APPENDIX 3. TIME AND EVENT SCHEDULE

TEST/APPLICATION	SAMPLE	SCR	Day 0					Day 1				Day 2				Day 3				Discharge day	Day 7	Day 14	Day 21	Day 28	F/U for sequeale*****								
			H0	H4	H8	H12	H18	H24	H30	H36	H42	H48	H54	H60	H66	H72	H78	H84	H90		**** ***	**** ***	**** ***	**** ***	Month 3	Month 6	Month 12						
Informed Consent		X																															
Demographic/ drug history		X																															
Medical history		X																													X	X	X
Temperature*		X	X	X	X	X	X	X	X	X	X	X	X	X	X	X	X	X	X			X	X	X	X	X	X	X	X	X	X	X	X
Vital signs**		X	X	X	X	X	X	X	X	X	X	X	X	X	X	X	X	X	X			X	X	X	X	X	X	X	X	X	X	X	
Weight/Height		X																															
Physical examination		X					X				X				X						X	X	X	X	X	X	X	X	X	X	X	X	
Neurological exam																				X					X	X	X	X	X	X	X	X	
Symptom questionnaire			X				X				X				X						X	X	X	X	X	X	X	X	X	X	X	X	
Randomisation			X																														
Injectable artesunate***			X			X	X																										
Oral ACT****									(X)		(X)				(X)				(X)														
SAMPLE COLECTION																																	
Malaria RDT		X																															
Malaria blood film*****	EDTA	X	X	X	X	X	X	X	X	X	X	X	X	X	X	X	X	X	X	X	X	X	X	X	X	X	X	X	X	X	X	X	
Haematocrit*****	EDTA	X	X	X	X	X	X	X	X	X	X	X	X	X	X	X	X	X	X	X	X	X	X	X	X	X	X	X	X	X	X	X	
Haemoglobin	EDTA		X				X				X				X						X					X	X	X	X				
Blood glucose*****			X	(X)	(X)	(X)	(X)	(X)																									
Full Blood Count	EDTA		X				X				X				X						X					X	X	X	X				
Biochemistry*****	EDTA		X				X				X				X						X					X	X	X	X				
Reticulocytes	EDTA		X				X				X				X						X					X	X	X	X				

*Temperature measured at time of malaria blood film until 2 consecutive measurements below 37.5°C

**Vital signs recorded hourly for unstable patients, then 6 hourly for stabilised patients, and at each F/U visit.

***Injectable artesunate at 0, 12, 24 hrs and until able to tolerate oral medication

**** Oral ACT starts 8 hours after the last dose of iv artesunate. ACT for 3 days, first dose directly observed and then DOTs on study wards if patient agrees, or patient can be discharged to complete treatment at home.

*****Malaria blood film and HCT taken at admission and 0h, 4h, 8h and 12h, then +6 hourly until H48, then 12 hourly until 2 consecutive negative slides, day 7, 14, 21, 28, and unscheduled (n).

*****Blood glucose measured on admission and between 4 and 6 hourly thereafter for at least 24 hours or until the patient recovers consciousness and can eat if longer than 24 hrs.

*****Biochemistry assessments including bilirubin, ALT, AST, Alkaline Phosphatase, and creatinine levels, LDH and any other tests that might be deemed relevant by the treating physician.

*****The time-window for the visit on Day 7, 14, 21 is +/-3 days and for the visits on Days 28 is -3/+7 days.

*****Longer term follow up only of patients who are not fully recovered by D29

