5.4.3. Exploratory endpoints

- (1) Parasite clearance half-life and other parasite clearance parameters (PC50, PC90, 12-hour parasite reduction ratio) compared between 1-step vs. conventional 2-step parenteral artesunate formulations.
- (2) Time from start parenteral treatment to follow up treatment with an oral ACT (recovery to per os treatment) of 1-step vs. conventional 2-step parenteral artesunate formulations.
- (3) Fever clearance time (i.e. the time taken for the tympanic temperature to fall below 37.5°C and remain there for at least 24 hours) of 1-step vs. conventional 2-step parenteral artesunate formulations.
- (4) Incidence of adverse events and serious adverse events by study arms within the first 28 days.

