6.2.3. Physical Examination and Vital Signs

Physical examination will be conducted by a qualified study team member. Weight, height, pulse rate, blood pressure, respiratory rate, temperature, and spleen and liver size will be recorded if palpable. Non-invasive neurological exams will be performed to monitor recovery and neurological sequelae. This will be done before discharge from the study ward, on day 28 of follow up. And, for participants who have sequelae at day 28, neurological exams will be done at month 3, month 6, and month 12.

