6.4. Procedures during hospitalisation

A physical examination will be performed daily and every six hours on indication. Vital signs recorded hourly for unstable patients, then 6 hourly for stabilised patients, and at each FU visit. A symptom questionnaire will be taken daily to help identify adverse events. All studies procedure will follow appendix 3.

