6.6.2. During hospitalisation

During hospitalisation, patients will have blood taken for malaria films and haematocrit at 4h, 8h and 12h and thereafter every 6 hours until parasite clearance (when two consecutive malaria slides are negative). Haematocrits will be done whenever a malaria blood film is made.

During hospitalisation (24 hr, 48 hr 72 hr and 96 hr and follow-up visits (day 7, 14, 21, 28), blood will also be taken for:

- 1 mL EDTA: Full blood count, , and Hb
- Reticulocyte count
- 1 mL heparinised blood: biochemistry assessments including bilirubin, ALT, AST, Alkaline Phosphatase, and creatinine levels, and LDH.

Other tests that might be deemed relevant by the treating physician for the care of the patients can be performed.

Note: Once parasitemia has been cleared and the patient tolerates oral antimalarial medications. The patients can be discharged according to the judgement of treating physician.

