3.4 Fever clearance and parasite clearance during treatment, by treatment allocation

Table 4 Clinical recovery*, fever clearance, and parasite clearance by study arm**

	1-STEP AS N=XXX	2-STEP AS N=XXX	Both groups N=XXX	P- value (2-sided)
Hours to fever clearance, mean (SD) (baseline to start of first 24h period <37.5C; temperature was recorded every 4 hours, until day 2, then 6 hourly)				
DRC	XX.X (X.X)	XX.X (X.X)	XX.X (X.X)	X.XXX
Tanzania	XX.X (X.X)	XX.X (X.X)	XX.X (X.X)	X.XXX
All study sites	XX.X (X.X)	XX.X (X.X)	XX.X (X.X)	X.XXX
Day 3 blood smear still positive, n/N (%)** (taking prior clearance or discharge as negative)				
DRC	XX/XXX (XX)	XX/XXX (XX)	XX/XXX (XX)	X.XXX
Tanzania	XX/XXX (XX)	XX/XXX (XX)	XX/XXX (XX)	X.XXX
All study sites	XX/XXX (XX)	XX/XXX (XX)	XX/XXX (XX)	X.XXX
Hours to tolerate oral medication, mean (SD)* (baseline to start of oral ACT)				
DRC	XX/XXX (XX)	XX/XXX (XX)	XX/XXX (XX)	X.XXX
Tanzania	XX/XXX (XX)	XX/XXX (XX)	XX/XXX (XX)	X.XXX
All study sites	XX/XXX (XX)	XX/XXX (XX)	XX/XXX (XX)	X.XXX
Parasite clearance half-life in hours, mean (SD)** (excluding patients with initial count insufficient to estimate half-life)				
DRC	X.X (X.X)	X.X (X.X)	X.X (X.X)	X.XXX
Tanzania	X.X (X.X)	X.X (X.X)	X.X (X.X)	X.XXX
All study sites	X.X (X.X)	X.X (X.X)	X.X (X.X)	X.XXX

*Protocol recommends patients receive a minimum of 3 doses of injectable artesunate before switch to oral ACT. Patients may vary if discharged before 24 hours, died, or referred.

** Parasite dynamics will be affected by patients who are transfused.

STATISTICAL ANALYSIS PLAN
3.5 Safety assessments and tolerability (Incidence of adverse events and serious adverse events by study arms within the first 28 days)

Safety analyses will be based on the whole population that get administered the study drug. That is, the safety and tolerability data will be pooled from all the sites that received the same antimalarial treatment.

The safety and tolerability of 1-STEP AS versus 2-STEP AS will be assessed by comparing the frequency (%) of adverse events and serious adverse events, with particular attention to the variables listed below, which pertain to severe malaria.

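### Temperature recording may stop after two readings under 37.5°C, so the schedule does not secure the 24 hours of data that the fever-clearance endpoint requires

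*Protocol*

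**What the plan says.** Protocol section 5.4.3 lists fever clearance time as its third exploratory endpoint: "the time taken for the tympanic temperature to fall below 37.5°C and remain there for at least 24 hours". SAP section 2.1.3 keeps the definition but places it among the secondary endpoints. SAP Table 4 (section 3.4) counts hours from baseline to the start of the first such 24-hour period, and reports mean (SD) and p-values by site and overall.

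The documents describe temperature collection in three ways:

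- **Protocol Appendix 3, single-asterisk footnote:** "Temperature measured at time of malaria blood film until 2 consecutive measurements below 37.5°C". The film times it depends on are four-hourly to H12, "then +6 hourly until H48, then 12 hourly until 2 consecutive negative slides".
- **SAP Table 4:** "temperature was recorded every 4 hours, until day 2, then 6 hourly", with no stopping rule.
- **Protocol section 6.4, repeated in Appendix 3:** "Vital signs recorded hourly for unstable patients, then 6 hourly for stabilised patients, and at each FU visit". This has no stopping rule tied to fever, but does not say whether vital signs include temperature. Section 6.2.3, on physical examination and vital signs, does list it: "Weight, height, pulse rate, blood pressure, respiratory rate, temperature, and spleen and liver size will be recorded if palpable".

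The film schedule itself has two versions. Section 6.6.2 has films at 4, 8 and 12 hours and "thereafter every 6 hours until parasite clearance". Appendix 3 and the blood-volume table in section 6.6.3 go to 12-hourly after H48.

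**The concern.** An endpoint defined by 24 hours under a threshold needs readings that cover 24 hours. A rule that ends measurement at the second low reading cannot supply them. A site that follows the footnote literally would hold, for each child, a record that stops well inside the window that the SAP needs to examine. Readings not taken cannot be recovered at analysis.

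The SAP note adds a reporting problem. It would describe in the results table a measurement frequency that no protocol schedule requires.

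**Working it through.** No figure in the plan depends on this point, so there is nothing to reproduce. The check is how much of 24 hours each schedule observes.

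**Inputs.** Required window: 24 h (Protocol 5.4.3; SAP Table 4). Stop: second consecutive reading under 37.5°C (Appendix 3 temperature footnote). Reading times: H0, 4, 8, 12, then 6-hourly to H48, then 12-hourly (Appendix 3 film footnote).

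**Step 1: span of the two readings that end recording.** Share observed = gap ÷ 24; unobserved = 24 − gap.

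| Period | Gap | Share of 24 h | Unobserved |
|---|---|---|---|
| H0 to H12 | 4 h | 4/24 = 17% | 20 h |
| H12 to H48 | 6 h | 6/24 = 25% | 18 h |
| After H48, Appendix 3 | 12 h | 12/24 = 50% | 12 h |
| After H48, section 6.6.2 | 6 h | 6/24 = 25% | 18 h |

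No row reaches 24 h.

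**Step 2: readings needed to span at least 24 h.**

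- Appendix 3, low run starting at H0: H0, 4, 8, 12, 18, 24 = 6 readings, so 6 − 2 = 4 are not required by the footnote.
- Starting at H12: H12, 18, 24, 30, 36 = 5 readings; 5 − 2 = 3 are not required.
- Starting at H48, 12-hourly: H48, 60, 72 = 3 readings; 3 − 2 = 1 is not required.
- SAP frequency: 24/4 + 1 = 7 readings while 4-hourly, 24/6 + 1 = 5 once 6-hourly.
- Vital-sign rounds, 6-hourly: 24/6 + 1 = 5 readings.

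Example: low readings at H12 and H18 end recording under the footnote. A temperature at or above 37.5°C at H24, H30 or H36 would break the 24-hour period, but no reading is required at those times.

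**Step 3: compare the SAP note with the protocol.** The SAP has 4-hourly readings up to day 2, which Appendix 3 places at H48. Appendix 3 is 4-hourly only to H12. The two therefore differ from H12 to H48, and the SAP has no stopping rule.

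**Step 4: can the vital-sign rounds be relied on?** Appendix 3 gives temperature and vital signs separate rows and separate footnotes. The listing of temperature in section 6.2.3 falls under section 6.2, which covers screening, eligibility and baseline. Section 6.4 sets the 6-hourly rounds and then defers to Appendix 3. Section 6.5 says that monitoring is not strictly defined, with blood glucose as the exception, and that monitored parameters will vary slightly by site. Nothing here confirms temperature at every in-hospital round, and nothing rules it out.

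**Step 5: how else can follow-up end?** Section 6.6.2 lets the physician discharge a child once parasites have cleared and oral treatment is tolerated; it sets no afebrile period. A note to SAP Table 4 recognises early discharge, death and referral, but the SAP gives no rule for handling such children in fever clearance, and a mean (SD) cannot use incomplete times.

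**The case against.** The strongest reply is that the data will probably exist. Vital signs are taken at least 6-hourly without a stopping rule tied to fever, temperature is a vital sign in ordinary ward practice, and section 6.2.3 names it under that heading. The Appendix 3 grid also marks temperature at each time point to H90 and at follow-up visits, which fits poorly with an absolute stop. The footnote may limit only the readings taken with films. If so, five rounds cover 24 hours, and without the stop the grid could confirm clearance starting as late as H90 − 24 = H66. This reply stands as a possible reading, but the documents do not settle it.

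A reader might infer three stronger things, none of them supported:

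- **That the endpoint is impossible to compute, or that every child will lack the data.** If the rounds include temperature, it can be computed for children still in hospital.
- **That clearance will be dated too early.** No passage counts two low readings as clearance. Under the SAP rule such a child would have an unconfirmed time, not an early one.
- **That a stated share of returning fevers would be missed.** The documents give no rate for fever returning after two low readings, and serial temperatures in one child are correlated, so no percentage can be derived.

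It is also fair to say that the same rule applies to both arms and that section 3.2 states the study is not powered for formal comparison of efficacy outcomes.

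**Conclusion.** The inconsistency is real, and the protocol and SAP should be reconciled. Taken alone, the temperature footnote observes 17% to 50% of the required 24 hours, leaving 12 to 20 hours uncovered. The SAP assumes a schedule that the protocol does not contain. Whether the data will exist depends on whether in-hospital vital signs include temperature, which the documents leave open.

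The size of the gap rests on the Appendix 3 film times and on reading the footnote as an actual stop. The consequence is limited to fever clearance, whose status also differs between the documents. Neither co-primary endpoint nor the sample size is affected. The change is worth making because it is cheap before data collection and cannot be made afterwards.

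**What to change.** 1. **Appendix 3 temperature footnote:** record temperature at the existing 6-hourly vital-sign rounds until it has stayed under 37.5°C for 24 hours or the child leaves hospital.
2. **SAP Table 4 note:** state the same schedule.
3. **SAP analysis:** censor children discharged or referred before 24 afebrile hours. Replace mean (SD) with a time-to-event summary, for example a Kaplan-Meier median and log-rank test. Name the censoring time, since the event is dated to the start of the 24-hour period, and state how deaths are handled. Discharge is likely to be related to recovery, so report the number censored in each arm.
4. **Film schedules after H48:** reconcile section 6.6.2 with section 6.6.3 and Appendix 3.

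The cost is a few extra readings at rounds already scheduled, one protocol footnote, the film-schedule wording, and a small SAP change.

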APPENDIX 4. TREATMENT GUIDELINES FOR SEVERE MALARIA

Introduction

Severe *falciparum* malaria is a medical emergency. Mortality is high and most deaths occur within 24 hours after admission to the hospital. Cerebral malaria, the most prominent manifestation of severe malaria carries a 16-20% mortality, but once multiple vital organ dysfunction occurs, the figure increases to as high as 30% (WHO 1990, 2000). The clinical manifestations depend on age. Hypoglycaemia, convulsions, and severe anaemia are relatively more common in children; acute renal failure, jaundice, and the acute respiratory distress syndrome (ARDS) are more common in adults. Cerebral malaria (with coma) and a severe metabolic (lactate) acidosis may occur at any age, and the severity of both features is a strong prognostic factor for a fatal outcome.

Cerebral malaria is characterized by coma of varying depth, usually with no focal signs. Convulsions occur in up to 80% of cases in children, but in less than 10% of adults. If the patient survives, there are usually (>90%) no neurological sequelae. Unlike in septicaemia, circulatory shock ('algid malaria') is not common in severe malaria. If hypotension is present, one should consider concomitant (gram negative) septicaemia or meningitis. Also, leucocytosis is not common in malaria, although it can be present in very severe disease. Leucocytosis with a shift to the left, should trigger the possibility of concomitant bacterial infection. Thrombocytopenia is always present in severe malaria, but this is seldom accompanied by bleeding problems. Diffuse intravascular coagulation (DIC) is rare (less than 5% of severe cases), and can cause serious bleeding. Black water fever is a rare complication of *falciparum* malaria, with severe intravascular haemolysis and haemoglobinuria. It is associated with the use of quinine and G-6-PD deficiency. About 10% of these patients have oliguric renal failure (Tran 1996). Table 1 gives a brief summary of the manifestations of severe malaria.

Diagnosis and differential diagnosis

In patients presenting with symptoms compatible with severe malaria, the diagnosis should be confirmed by a peripheral blood slide, or by rapid test based on the detection of the malaria antigen HRP2 (e.g., Paracheck-F test). The sensitivity of these rapid antigen test is high (97%), meaning that a negative test almost excludes the diagnosis *falciparum* malaria. However, the specificity depends on the endemicity of the disease, since the test can remain positive for a few weeks after a malaria attack. Especially in highly endemic areas a positive test can thus be caused by a recent malaria episode, whereas the cause of the presenting fever can be a different one. The specificity of the test in non-endemic countries can be as high as 100% but drops to 85% in malaria endemic areas. A positive malaria slide, especially in the adult patient, does not prove that the presenting symptoms are caused by severe malaria, because of the high background prevalence of peripheral blood parasitaemia. Other causes of coma have thus also to be considered, including: hypoglycaemia, meningitis, septic shock and post-ictal coma (after febrile convulsion). Moreover, sedative drugs, severe anaemia, severe acidosis or severe hyponatraemia can contribute. All these factors (except meningitis and sedative drugs) can occur as a complication of severe malaria. Consequently, blood glucose and Haematocrit should be checked in every patient (i-STAT or glucose-stick), a lumbar puncture should be performed, and the blood pressure has to be measured. If available electrolytes and acid-base status should be checked. The treatment of these conditions is described below

Antimalarial treatment

The mainstay of the treatment of severe malaria is the immediate start of parenteral antimalarial treatment. The available antimalarial drugs to treat severe malaria are parenteral quinine and the parenteral artemisinin derivatives (artesunate).

Artesunate belongs to the most rapidly acting and potent group of antimalarial drugs (artemisinin derivatives). They are safer and easier to administer compared to quinine. Artesunate and artemether are used widely in SE Asia, and increasingly in sub-Saharan Africa, for the treatment of uncomplicated and severe malaria as alternatives to quinine (Van Aghtmael 1999). Injectable artesunate, which is water soluble, can be given intravenously and gives very reliable plasma levels. The dose of artesunate is 2.4 mg/kg i.v. or i.m. on admission, 12 hours, 24 hours, and then daily. Children <20 kg will get 3.0 mg/kg. If possible, to take oral medication, the patient can switch to an oral course of Coartem (dosing see above). The artemisinin derivatives have remarkably few side effects. Allergic skin reactions and anaphylaxis have been reported.

Treatment of specific complications.

Generally, all patients who are in a critical condition (i.e., their survival is questionable) on admission should be transferred immediately to the intensive care unit. Patients who have been admitted to the ward and who show signs of deterioration which endangers their survival should be transferred from the ward to the ICU.

Fluid management

Severe malaria is a multi-organ disease, and supportive treatment for all kinds of organ failure can be indicated. *Fluid management* can be difficult. The patient is usually dehydrated on admission, and should be rehydrated to support the already compromised microcirculation. Hyponatraemia is common, and mainly a consequence of dehydration. Dextrose-Saline can be used for rehydration, and not only dextrose solutions. (Saline without dextrose can be used in adults but should never be used in paediatric patients.) Dextrose solutions without any NaCl will further lower the plasma sodium concentration, and will inadequately rehydrate the patient. However, there is a strong tendency to develop pulmonary oedema, so care should be taken to avoid too aggressive fluid infusion.

Hypotension is not a common feature of severe malaria and in case of circulatory shock, concurrent septicaemia should be considered. Blood cultures should be taken and the patient should be treated empirically with antibiotics, covering gram-negative bacteria (e.g., the combination of cefotaxime and gentamicin). In case of hypotension, the patient should receive fluid resuscitation. Systemic salmonella infection may develop, presumably because of increased translocation of bacteria in the gut (Mabey 1987). If the patient has been admitted for several days in the ICU, hospital acquired infections should also be considered. Secondary pneumonia is common.

Acidosis in severe malaria can be due to acute renal failure, but usually is a lactic acidosis resulting from tissue hypoxia, generally in the absence of hypotension. Treatment should therefore be directed to optimize the microcirculation, but we have only limited tools to achieve this. Prompt treatment of the parasite causing sequestration and obstruction in small vessels, optimal fluid management and treatment of severe anaemia can all contribute. Using iSTAT results can help in the management of acidosis. If the arterial pH drops below 7.2, 100 ml 8.4% HCO₃ over 30 minutes can be given.

Anaemia is a frequent feature, especially in young children with severe malaria. Transfusion of packed red cells can be restricted to those with haematocrit falling below 20%. It is essential that blood products are negative for transmissible diseases like HIV, hepatitis B, hepatitis C and syphilis.

Disseminated Intravascular Coagulation (DIC)

For those rare patients who develop DIC with bleeding, fresh frozen plasma can be given. In addition, vitamin K should be administered, in a daily dose of 10 mg slowly i.v., for 3 days.

Coma

Hypoglycaemia as a cause for convulsions should be ruled out. A lumbar puncture should be considered. The usual nursing care for the unconscious patient should be applied. If available a nasogastric tube should be inserted and the stomach contents let out. To decrease the chances of aspiration, enteral feeding should not be started on the first day of admission. The patient should be turned every 2 hours to prevent bedsores. If possible, it is preferable to insert a urethral ('Foley') catheter to prevent maceration of the skin and for monitoring fluid management. Eyes should be kept irrigated with saline or artificial tears and the lids kept closed with eye pads. The severity of coma should be graded using the Glasgow coma scale for adults and the Blantyre coma scale for children. Deterioration in the coma score should be reported immediately to the physician on call.

Convulsions are very common in children with cerebral malaria. As for coma, hypoglycaemia as a cause for convulsions should be ruled out. A lumbar puncture should be considered. In adults, convulsions are relatively rare, so that prophylaxis is not generally recommended. If seizures occur, they should be treated promptly with intravenous benzodiazepines (adults 10 mg iv, children 0.3 mg/kg). Since children are prone to febrile convulsions, treatment to reduce fever (paracetamol, cold sponging, etc.) should be given if the rectal temperature is above 39°C.

Hypoglycaemia is particularly common in children and pregnant women with malaria, and, as mentioned above, with the use of quinine. It can be treated with 1 ml/kg of a 50% glucose solution.

Oliguric renal failure is a common complication of severe malaria in adults. However, occasionally the renal failure is non-oliguric. If the adult patient is oliguric (< 20 ml per hour), this can be caused by dehydration or acute tubular necrosis. Dehydration requires rehydration with normal saline, whereas acute tubular necrosis (ATN) requires dialysis and carries the danger for fluid overloading since the patient is not likely to restore diuresis with appropriate clearance during the following 2 to 5 days. The clinical assessment of the hydration status (skin turgor, dry lips and mouth, tears, jugular venous pressure). If there is still no diuresis after adequate rehydration, furosemide can be given in increasing doses 40mg-100mg-200mg-400mg at half hour intervals. This will not improve renal function, but if diuresis is still absent after this procedure, it is likely that the patient has ATN.

Acute respiratory distress syndrome (ARDS) is a feared complication of mainly adult severe malaria. The chest X-ray will generally show diffuse shadowing of the lung fields. In case of respiratory distress, the patient should be propped upright and receive oxygen therapy (nasal catheter or face mask). Furosemide should be tried to lower the venous pressure, but this will not often relieve symptoms, since the pathogenesis is capillary leakage and not fluid overload *per se*.

Blackwater fever with severe intravascular haemolysis can cause severe anaemia requiring transfusion. On theoretical grounds alkalinisation of the urine can be recommended in this condition, although no clinical studies are available.

Conclusions.

A patient with severe *falciparum* malaria with multiple organ failure is a challenge for the treating physician. If the patient, often a young individual, survives, there are usually no sequelae. Prompt diagnosis and start of antimalarial treatment are essential. But good supportive treatment, realizing the common complications of the disease, is equally important.

Table 1 Brief summary of the manifestations of severe malaria.

Manifestations of severe malaria	Pathophysiology	Treatment
Coma	Compromised microcirculation, other factors like local nitric oxide overproduction?	Good nursing care. Lumbar puncture to rule out meningitis. Rule out hypoglycaemia.
Convulsions	Compromised microcirculation, Hypoglycemia.	Diazepam, phenobarbitone, phenytoin Lumbar puncture to rule out meningitis. Rule out hypoglycaemia.
